Brief Pain inventory (BPI)		X		X		X	X	X	X	X	X
Ketamine Infusion			X								
Pupillometry****			X	X		X	X	X	X	X	
Implicit Association Test-IAT		X		X					X		
Randomization (buprenorphine/placebo)				X							
Buprenorphine 0.2mg-0.8mg (10 SL/wk) Dispensed***				X		X	X	X			
Ketamine & Metabolites Blood Levels**			X								
Buprenorphine & Metabolites Blood Levels							X		X		
Prolactin Blood Levels			X **			X	X	X	X	X	
Clinician-Administered Dissociative States Scale (CADSS)**			X								
Visual Analogue Scale (VAS)**			X								
Subjective Opiate Withdrawal Scale (SOWS)										X	X
Clinician Opiate Withdrawal Scale (COWS)										X	X
Concise Health Risk Tracking Scale Self-Report (CHRT-SR)		X					X		X	X	X
Adverse Event Review		X	X	X	X	X	X	X	X	X	X
Concomitant Medication Review	X	X	X	X	X	X	X	X	X	X	X

*if no results within the past 6 months

**-.5 min, 40, 80, 120, 180, 220 min

*** Weekly supply of rx provided. Varying dosage depending on response & tolerability.

****-.5min, 40 min

***** @220 min / discharge

2. Introduction:

2.1. Background:

Opiate abuse and addiction have become major public health problems in the United States over the past decade (1). The profound increase in accidental deaths due to opioid overdose is accompanied

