24. Current (or chronic) use of opiates.
25. Current use of Lamictal and an inability to stop the medication prior to receiving ketamine.

5.3. Screen Failure:

Screen failures are defined as participants who consent to participate in the screening portion of the study (i.e., sign our screening ICF) but are not subsequently randomly assigned to the study intervention or entered in the study. A minimal set of screen failure information is required to ensure transparent reporting of screen failure participants, to meet the Consolidated Standards of Reporting Trials (CONSORT) publishing requirements and to respond to queries from regulatory authorities. Minimal information includes demography, screen failure details, eligibility criteria, and any serious adverse event (SAE).

Individuals who do not meet the criteria for participation in this trial (screen failure) due to a specific modifiable factor may be rescreened at a later date once appropriate study criteria are met. Rescreened participants will be assigned the same participant number as for the initial screening.

In the case of screen failure, screening data of such patients will be electronically stored in our REDCap database.

6. Study Intervention:

Patients will receive an infusion of ketamine at 0.5mg per kg over 40 minutes. Ambient light will be lowered and patients are accompanied during and after the completion of the infusion until discharge. Patients will be assessed clinically at 3 hours and then at day 3. After the ratings are completed on Day 3, patients will be started on sublingual medication—buprenorphine or matched placebo beginning at 0.2 mg per day. Patients will be assessed weekly for 4 weeks. Doses will be adjusted at each session to a maximum of 0.8 mg after 3 weeks. Increases will be by 0.2mg increments. Participants will receive their study medication during weekly visits and will be instructed to self-administer it at home, ensuring the drug fully dissolves within 20 minutes before ingestion. As with our previous ketamine study, patients will be asked to maintain their other medications throughout the study as feasible. At the end of the active treatment phase, patients will discontinue the study drugs and will be followed up on Days 38 and 45 to monitor for any signs of withdrawal.

7. Participant discontinuation/withdrawal

7.1. Discontinuation of Study Intervention:

Subjects may be withdrawn from the study by the Principal Investigator if a subject:

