- Is non-adherent with study procedures
- The randomization code is broken for the subject

The Principal Investigator may also withdraw a subject if he/she believes that for safety reasons it is in the best interest of the subject to be withdrawn.

Discontinuation information [e.g., date and the reason(s) for discontinuation] will be recorded in the subject's CRF (i.e., Study Completion Form) and relevant forms on REDCap.

Subjects withdrawn from the study due to an AE will be followed up for 30 days or until resolution. Subjects withdrawn from the study will be replaced if withdrawal occurs prior to the completion of the first treatment day (Visit 3). Should a participant fail to return for required visits or drops out of the study, an effort will be made to determine why. This information will subsequently be recorded on the subject's CRF and relevant forms on REDCap.

Subjects will be encouraged to remain adherent with all expected study visits. Non-adherence to expected study visits will be documented and may result in removal from the study. This will be clearly discussed during the informed consent process and reinforced throughout the study through regular screening for issues with compliance.

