7.2. Participant Discontinuation/Withdrawal from the Study

An investigator may discontinue or withdraw a participant from the study for the following reasons:

- Pregnancy
- Significant study intervention non-compliance
- If any clinical adverse event (AE), laboratory abnormality, or other medical condition or situation occurs such that continued participation in the study would not be in the best interest of the participant
- Disease progression which requires discontinuation of the study intervention
- If the participant meets an exclusion criterion (either newly developed or not previously recognized) that precludes further study participation

The reason for participant discontinuation or withdrawal from the study will be recorded on the REDCap e-CRF.

Subjects may withdraw voluntarily from the study at any time.

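### Section 7 does not separate stopping study drug from leaving the study, so early stoppers who leave get adverse-event follow-up but no scheduled SSI, C-SSRS, COWS or SOWS ratings

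*Combined protocol and SAP*

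**What the plan says.** The headings of Sections 7.1 and 7.2 distinguish the intervention from the study, but the text beneath them does not.

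- **Section 7.1** opens with "Subjects may be withdrawn from the study by the Principal Investigator if a subject" meets one of two grounds: "Is non-adherent with study procedures" or "The randomization code is broken for the subject". The investigator may also withdraw a subject for safety. What is to be recorded is discontinuation information, with date and reasons as the examples.
- **Section 7.2** gives one list of reasons for leaving the study. Two of them concern the drug: "Significant study intervention non-compliance" and "Disease progression which requires discontinuation of the study intervention".
- **Follow-up after leaving.** Section 7.1 says "Subjects withdrawn from the study due to an AE will be followed up for 30 days or until resolution". Section 8.3.1 sets a 30-day adverse-event follow-up period after the last visit. Sections 8.3.4 and 8.3.5 set capture windows of 7 days for non-serious events and 30 days for serious ones. None of these names a scale.
- **Section 6** ties off-drug monitoring to the end of the four-week phase: "At the end of the active treatment phase, patients will discontinue the study drugs and will be followed up on Days 38 and 45". The Schedule of Activities (Section 1.5) places COWS and SOWS on those two days only and has no early-termination column.
- **Section 9** fits the primary mixed model to all available SSI scores, assumes data missing at random, and describes withdrawal symptoms and off-drug suicidality at Days 38 and 45.

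**The concern.** A decision about the drug can become an exit from the study. A broken code or missed doses may be a reason to stop tablets, but neither makes an SSI score unobtainable. When these grounds are applied, scores that could have been collected are not, and the primary model would have used them. Day 31 is always among the scores lost. Anyone removed before Day 10, the first SSI on study drug, has no active-phase SSI and so falls outside the mITT set altogether.

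The safety side matters as well. Section 1.3 gives discontinuation symptoms and the return of suicidal ideation as the purpose of the two-week follow-up. Section 2.1 remarks that the earlier low-dose buprenorphine trial made no formal assessment of withdrawal. As written, those outcomes would be described only for participants still attending at Days 38 and 45.

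**Working it through.** The plan states no figure on this point to reproduce. The check compares the text of Section 7 with the visit days in the Schedule.

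**Inputs (Schedule, Section 1.5, nominal days).** Randomization and first dose: Day 3. SSI after randomization: Days 10, 17, 24, 31, 38, 45, so 6 visits, of which 4 (Days 10 to 31) are in the treatment phase. C-SSRS: the same days plus the Day 5 telephone contact, so 7. COWS and SOWS: Days 38 and 45, so 2. Assumption: the last dose is taken on the day of the stop visit.

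**Formulas.** Ratings lost = scheduled ratings after the stop day. Delay to the first COWS/SOWS for someone kept on the calendar = 38 − stop day.

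| Stop day | SSI lost, of 6 | C-SSRS lost, of 7 | Treatment-phase SSI lost, of 4 | COWS/SOWS lost, of 2 | Delay if kept on calendar |
|---|---|---|---|---|---|
| 10 | 5 | 5 | 3 | 2 | 38 − 10 = 28 days |
| 17 | 4 | 4 | 2 | 2 | 38 − 17 = 21 days |
| 24 | 3 | 3 | 1 | 2 | 38 − 24 = 14 days |
| 31 (completer) | 0 | 0 | 0 | 0 | 38 − 31 = 7 days |

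The completer's second rating is at 45 − 31 = 14 days. The loss columns apply to a participant who leaves; the last column applies to one who stops drug but stays.

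**Adverse-event cover after leaving at Day 17.** Non-serious capture runs to 17 + 7 = Day 24. Serious-event capture and the 30-day follow-up run to 17 + 30 = Day 47, or until resolution for adverse-event withdrawals. Events are recorded, but no scale is scheduled.

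**Dose at the stop (Section 6).** 0.2 mg from Day 3, then steps of 0.2 mg at weekly visits. A Day 17 stopper has had at most 0.4 mg per day, against up to 0.8 mg for a completer. Early stoppers are therefore not claimed to be more prone to withdrawal symptoms.

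**Can last-dose timing use existing visits?** Stop day + 7 and + 14 gives Days 17 and 24 for a Day 10 stop, Days 24 and 31 for Day 17, and Days 31 and 38 for Day 24. All are scheduled visits.

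**Scale.** The plan gives no early-stopping rate. Each assumed 10% is 0.10 × 60 = 6 participants, about 3 per arm at equal rates; 20% would be 12 and 30% would be 18.

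**The case against.** The strongest reply is that both lists are permissive and that nothing equates stopping drug with leaving. The adverse-event ground in 7.2 applies only where continued participation is against the participant's interest, which is close to the exception proposed below. That narrows the problem mainly to a broken code, drug non-compliance and progression needing a drug stop. This is fair, but discretion to remove is not a rule to retain, and no text describes the path in which a participant stops drug and stays.

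Some of the lost scores would be lost under any wording. People who miss visits, withdraw consent or cannot be reached often give no SSI, and Sections 7.1 and 7.3 already encourage attendance and require contact attempts. This stands: the claim covers obtainable scores only.

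Safety observation is not absent. Sections 8.3.4 and 8.3.6 follow events to resolution or stability, and withdrawal signs are a listed buprenorphine risk, so they can be recorded as adverse events. This also stands; the gap is in scheduled ratings.

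Off-drug scores might be said to change the question asked. They fit the question in Section 9, whose null hypothesis compares patients as randomized and whose model takes every available SSI.

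Finally, drug is taken at home, so stops can fall between visits. A last dose on Day 13 points to Days 20 and 27, both outside the ±2-day windows. Last-dose timing is then approximate.

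**Conclusion.** The concern holds. The text under 7.1 and 7.2 provides only for leaving the study, and a participant who leaves has no scheduled SSI, C-SSRS, COWS or SOWS rating afterwards. For a Day 17 stop the loss is 4 of 6 SSI visits (2 of 4 in the treatment phase, including Day 31), 4 of 7 C-SSRS assessments and both withdrawal ratings. Staying on the calendar alone would still put the first withdrawal rating at 21 days after the last dose instead of 7.

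These counts rest on nominal visit days and a last dose at the stop visit. How many participants are affected is unknown. Bias in the primary contrast is possible but not shown: removal driven by a recorded SSI score can be missing at random. The point is not fatal to the trial, but it should be fixed, because the plan allows primary and safety data to be given up without need.

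**What to change.** - In 7.1, state that a participant who stops study drug for any reason stays in the study unless they withdraw consent, are lost to follow-up, or the investigator judges that continued assessment itself is not in their interest.
- Continue SSI, C-SSRS, MADRS and adverse-event review on the existing calendar to Day 45.
- Add a Schedule footnote: rate COWS and SOWS at about 7 and 14 days after the last dose, at existing weekly visits where possible.
- In 7.1 and 7.2, remove a broken code and drug non-adherence as reasons to end follow-up. Keep the rules for when drug is stopped and the investigator's discretion to end participation for safety.

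The cost is protocol wording and one footnote, since the visits and scales already exist. The downside is a few off-drug visits, which some participants will decline.

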7.2. Participant Discontinuation/Withdrawal from the Study

An investigator may discontinue or withdraw a participant from the study for the following reasons:

- Pregnancy
- Significant study intervention non-compliance
- If any clinical adverse event (AE), laboratory abnormality, or other medical condition or situation occurs such that continued participation in the study would not be in the best interest of the participant
- Disease progression which requires discontinuation of the study intervention
- If the participant meets an exclusion criterion (either newly developed or not previously recognized) that precludes further study participation

The reason for participant discontinuation or withdrawal from the study will be recorded on the REDCap e-CRF.

Subjects may withdraw voluntarily from the study at any time.

7.3. Lost to Follow-up

A participant will be considered lost to follow-up if he or she fails to return for one scheduled visit and is unable to be contacted by the study staff.

We will take the following actions if a participant fails to return for a required study visit:

- We will attempt to contact the participant and reschedule the missed visit within 24 hours and counsel the participant on the importance of maintaining the assigned visit schedule and ascertain if the participant wishes to and/or should continue in the study.
- Before a participant is deemed lost to follow-up, the investigator or his designee will make every effort to regain contact with the participant (where possible, 3 telephone calls and, if necessary, a certified letter to the participant's last known mailing address or local equivalent methods). We will record these contact attempts in the participant's designated REDCap e-CRF.
- Should the participant continue to be unreachable, he or she will be considered to have withdrawn from the study with the primary reason of loss to follow-up.

8. Study Assessments and Procedures:

8.1. Efficacy Assessments:

Screening process:

Participants will be recruited through the Stanford Depression Research Clinic online recruitment pipeline (online portal for referrals). Potential participants will be prescreened through their medical records. Participants whose initial prescreening is consistent with study eligibility will then be invited to consent to and participate in screening with a study team member (over zoom) for further assessment of eligibility. In-depth screening will include demographics information; psychiatric and medical history; current and past medications with adequacy of trials assessed by the Massachusetts General Hospital (MGH) Antidepressant Treatment Response Questionnaire (ATRQ); psychiatric diagnoses via the Overview/History section of the Structured Clinical Interview for DSM-5 (SCID) and the Mini-International Neuropsychiatric Interview for DSM-5 (MINI); borderline personality disorder screener and diagnostic module from SCID for DSM-5 (if a participant meets the screening threshold on the self-reported pre-screening questions); suicidal ideations will be measured by the Scale for Suicidal ideation (SSI); depression assessment with the Hamilton Depression Rating Scale (17-item), and the Montgomery-Åsberg Depression Rating Scale (MADRS).

Participants will also be asked specifically about any significant neurologic disease, including dementia, Parkinson's or Huntington's disease, brain tumor, seizure disorder, subdural hematoma, multiple sclerosis, or history of significant head trauma; history of dementia or cognitive impairment; and whether they are receiving or planning to receive any other investigational treatments during this study. Screening will be performed by a consistent group of qualified study staff who have been trained and certified by the lab's Psychological Director to ensure fidelity to assessment procedures.

Screening must be completed within 2 weeks of formal study enrollment and baseline assessment, otherwise screening will need to be repeated prior to moving forward with enrollment and baseline assessment.

Efficacy assessments related to primary and secondary outcomes:

We will use the following clinical scales to quantify suicidal ideation: Scale for Suicide Ideation (SSI), Columbia-Suicide Severity Rating Scale (C-SSRS). General mood and anxiety will be quantified using the Montgomery Åsberg Depression Rating Scale (MADRS), and 21 items Hamilton Depression Scale (HAM-D-21).

8.2. Safety and Other Assessments:

All patients will undergo a clinical study visit with the study psychiatrist (or their designee) as part of the assessment for suitability in the study. This visit will include assessment of current psychiatric symptoms, psychiatric history (including past diagnoses, hospitalization, suicide attempts, past medication trials), current medical concerns (if any), past medical history, current medications, allergies, family psychiatric history, and social history. A mental status exam will be performed. Vital signs and certain studies (e.g., EKG, basic labs) will be obtained. Follow up clinical study visits will be performed.

8.3. Adverse Events and Serious Adverse Events:

8.3.1. Definition of Adverse Events:

An adverse event (AE) is any untoward, undesired, or unplanned event in the form of signs, symptoms, disease, or laboratory or physiological observations occurring in a person who has received study interventions. The event need not be causally related to the ketamine infusion or buprenorphine/placebo treatment in order to be considered an AE.

An AE includes, but is not limited to:

- Any adverse finding including a sign, symptom, abnormal assessment (laboratory test value, vital signs, electrocardiogram finding, etc.), or any combination of these.
- Any clinically significant worsening of a pre-existing condition;
- An AE that has been associated with a preexisting condition is a clinical condition (including a condition being treated) that is diagnosed before an informed consent form is signed and is documented as part of the subject's medical history.

The questions concerning whether the condition existed before the start of the active phase of the study and whether it has increased in severity and/or frequency will be used to determine whether an event is an intervention-emergent AE (IEAE).

An AE is considered to be intervention-emergent if [1] it was not present when the active phase of the study began and is not a chronic condition that is part of the subject's medical history, or [2] it was present at the start of the active phase of the study or as part of the subject's medical history, but the severity or frequency increased during the active phase.

For this study, the treatment follow-up period for adverse events is defined as 30 days following the last study visit.

Follow up will be documented in the subject's study file.

8.3.2. Definition of Serious Adverse Events:

A Serious Adverse Event (SAE) is defined as an AE that:

- Results in death
- Is life threatening (see below)
- Requires inpatient hospitalization or prolongation of an existing hospitalization (see below)
- Results in a substantial disruption of a person's ability to conduct normal life functions, i.e., the adverse event resulted in a significant, persistent or permanent change, impairment, damage or disruption in the patient's body function/structure, physical activities and/or quality of life
- Necessitates medical or surgical intervention to preclude such impairment
- Results in a congenital anomaly or birth defect

Additionally, important medical events that may not result in death, be life-threatening, or require hospitalization, may be considered SAEs, based upon appropriate medical judgment.

Life threatening refers to immediate risk of death as the event occurred or other medical intervention might have resulted in the death per the reporter. A life-threatening event does not include an event that,

had it occurred in a more severe form, might have caused death, but as it actually occurred, did not create an immediate risk of death.

Hospitalization is to be considered only as an admission. Hospitalization constitutes an AE to be classified as serious.

Note: Hospitalizations planned before the start of the study, for a preexisting condition that has not worsened, do not constitute an SAE (e.g., elective hospitalization for a total knee replacement due to a preexisting condition of osteoarthritis of the knee that has not worsened during the study).

If there is any doubt whether the information constitutes an SAE, the information will be treated as an SAE for the purpose of this study.

Timing for Reporting of Serious Adverse Events: Any SAE, regardless of causal relationship, will be reported to the Institutional Review Board (IRB), within 10 business days of the Principle Investigator learning of the event, by faxing or scanning a completed serious adverse event form to the assigned IRB panel. Follow-up information relating to an SAE will be reported to the IRB within 10 business days after the information is sent to the Principle Investigator. The subject should be observed and monitored carefully until the condition resolves or stabilizes or its cause is identified. All SAEs will be recorded in subject specific AE/SAE forms on REDCap and reviewed quarterly with the study DSMB.

8.3.3. Classification of an Adverse Event:

8.3.3.1. Severity:

All AEs will be assessed by the study clinician using the grading system defined below and recorded on designated REDCap subject-specific and study-wide AE logs.

- Mild – Events require minimal or no treatment and do not interfere with the participant’s daily activities.
- Moderate – Events result in a low level of inconvenience or concern with the therapeutic measures. Moderate events may cause some interference with functioning.
- Severe – Events interrupt a participant’s usual daily activity and may require systemic drug therapy or other treatment. Severe events are usually potentially life-threatening or incapacitating. Of note, the term “severe” does not necessarily equate to “serious”.

8.3.3.2. Relationship to Study Intervention:

All adverse events (AEs) must have their relationship to study intervention assessed by the clinician who examines and evaluates the participant based on temporal relationship and his/her clinical judgment. The degree of certainty about causality will be graded using the categories below.

Causal relationship options and definitions are as follows:

- Definitely related: Event can be fully attributable to administration of ketamine or buprenorphine.
- Probably related: Event is most likely to be explained by administration of ketamine or buprenorphine, rather than the subject’s clinical state or other agents/therapies.

- Possibly related: Event is as likely explained by administration of ketamine or buprenorphine, as by the subject's clinical state or other agents/therapies.
- Probably not related: Event is most likely to be explained by the subject's clinical state or other agents/therapies, rather than administration of ketamine or buprenorphine.
- Definitely not related: Event can be fully explained by the subject's clinical state or other agents/therapies, rather than the administration of ketamine or buprenorphine.

When assessing the relationship between an investigational product/protocol and an AE, the following parameters are considered:

- Temporal relationship between the administration of ketamine or buprenorphine and the AE
- Biologic plausibility of relationship
- Subjects' underlying clinical state or concomitant agents/therapies
- Where applicable, whether the AE abates on discontinuation of ketamine or buprenorphine (de-challenge)
- Where applicable, whether the AE reappears on repeat exposure to ketamine or buprenorphine (re-challenge)

SAEs that are not ketamine or buprenorphine related may nevertheless be considered by the Principal Investigator or the IMC to be related to the conduct of the study, i.e., to a subject's participation in the study.

8.3.3.3. Expectedness:

The study psychiatrist, in accordance with the listed risks on the study ICF, will be responsible for determining whether an adverse event (AE) is expected or unexpected. An AE will be considered unexpected if the nature, severity, or frequency of the event is not consistent with the risk information previously described for the study intervention.

8.3.4. Time Period and Frequency for Event Assessment and Follow-Up:

The occurrence of an adverse event (AE) or serious adverse event (SAE) may come to the attention of study personnel during study visits and interviews of a study participant presenting for medical care, or upon review by a study monitor.

All AEs including local and systemic reactions not meeting the criteria for SAEs will be captured on the appropriate case report form (CRF). Information to be collected includes event description, time of onset, clinician's assessment of severity, relationship to study product (assessed only by those with the training and authority to make a diagnosis), and time of resolution/stabilization of the event. All AEs occurring while on study must be documented appropriately regardless of relationship. All AEs will be followed to adequate resolution.

Any medical condition that is present at the time that the participant is screened will be considered as baseline and not reported as an AE. However, if the study participant's condition deteriorates at any time during the study, it will be recorded as an AE.

Changes in the severity of an AE will be documented to allow an assessment of the duration of the event at each level of severity to be performed. AEs characterized as intermittent require documentation of onset and duration of each episode.

Study psychiatrist will record all reportable events with start dates occurring any time after informed consent is obtained until 7 (for non-serious AEs) or 30 days (for SAEs) after the last day of study participation. At each study visit, the investigator will inquire about the occurrence of AE/SAEs since the last visit. Events will be followed for outcome information until resolution or stabilization.

8.3.5. Adverse Event Reporting:

AEs will be monitored continuously by designated study staff, recorded in applicable subject-specific and study wide REDCap eCRFs, and reported to the Stanford IRB annually.

Research staff will be trained to attend to signs of AEs and to report any potential unrelated or unexpected AE immediately to the PI. If AEs occur, appropriate medical and/or psychiatric care will be facilitated for the research participant, and recorded in the appropriate electronic AE logs on REDCap. As per Stanford IRB requirements, AEs will be reported to the IRB annually.

All subjects will have telephone and email contact information to reach the Principal Investigator and the Stanford IRB, in case of any distress or adverse response to the hypnosis or other components of the study.

An AE or SAE can occur from the time that the subject signs the informed consent form to 7 and 30 days, respectively, from the subject's last study visit regardless of relationship to the protocol. All AEs and SAEs will be recorded on the subject-specific and study wide eCRFs, which will be provided to the DSMB on a quarterly basis. The DSMB will instruct the Principal Investigator to follow all AEs, SAEs, and other reportable events until the event has subsided or values have returned to baseline, or in case of permanent impairment, until the condition stabilizes.

In addition to the information obtained from those sources, the subject will be asked the following nonspecific question: "How have you been feeling since your last visit?" Signs and symptoms will be recorded using standard medical terminology.

The following AE information will be included (when applicable): the specific condition or event and direction of change; whether the condition was preexisting (i.e., an acute condition present at the start of the study or history of a chronic condition) and, if so, whether it has worsened (e.g., in severity and/or frequency); the dates and times of occurrence; severity; causal relationship to the study interventions; action taken; and outcome.

8.3.6. Serious Adverse Event Reporting:

The PI or his designee will immediately report to the sponsor any serious adverse event (SAE), whether or not considered study intervention related, including those listed in the protocol or investigator brochure and must include an assessment of whether there is a reasonable possibility that the study intervention caused the event. Study endpoints that are serious SAEs (e.g., all-cause mortality) must be reported in accordance with the protocol unless there is evidence suggesting a causal relationship between the study intervention and the event (e.g., death from anaphylaxis). In that case, the investigator will immediately report the event to the sponsor.

All SAEs will be followed until satisfactory resolution or until the site investigator deems the event to be chronic or the participant is stable. Other supporting documentation of the event may be requested by the study sponsor and should be provided as soon as possible.

In case of SAEs, the study investigator will complete an Unanticipated Serious Adverse Event Form and submit to the study sponsor and to the reviewing Institutional Review Board (IRB) as soon as possible, but in no event later than 10 business days after the investigator first learns of the effect. The study sponsor will conduct an evaluation of an unanticipated adverse event and will report the results of such evaluation to the Food and Drug Administration (FDA) and to all reviewing IRBs and participating investigators within 10 business days after the sponsor first receives notice of the effect. Thereafter, the sponsor will submit such additional reports concerning the event as FDA requests. The Investigator will provide all relevant documentation pertaining to an SAE (e.g., additional laboratory tests, consultation reports, discharge summaries, postmortem reports, etc.) to the DSMB in a timely manner. Reports relative to the subject's subsequent course will be submitted to the DSMB until the event has subsided or, in case of permanent impairment, until the condition stabilizes.

Other reportable information, while not meeting the definition of an SAE, is reportable to the DSMB with the timeliness of an SAE.

This includes:

- Seizure
- Pregnancy occurring during the study period in which the subject was exposed to study intervention;
- Overdose (e.g., a dose higher than that prescribed by a healthcare professional for clinical reasons) with or without AEs;
- Abuse (e.g., use for non-clinical reasons) with or without an AE;
- Inadvertent or accidental exposure with or without an AE;

Designated study staff will be responsible for ensuring that unanticipated problems are reported to the IRB in compliance with their requirements for reporting serious and unexpected adverse events. Reporting will be conducted in compliance with guidelines specified by the Stanford University Research Compliance Office.

8.3.7. Reporting Events to Patients:

At enrollment, participants will be asked whether or not they would like to be informed about study outcomes. We will compile a list of those participants who would like to know about outcomes, and following study completion they will be individually emailed a copy of the study's primary outcome paper using individual, encrypted email.

We will closely monitor AE's on a continuous basis, and involve the DSMB in assessing whether any AE is unexpected, or more severe than expected (at a rate greater than what would be expected by chance). Should we identify any AE that meets one of those two criteria or should we have any unexpected SAE's we will notify currently enrolled participants, and change our consent to include the pertinent information.

8.3.8. Reporting Pregnancy:

We will not include pregnant women in this study. If the participant is of childbearing potential and not already pregnant, the participant must agree to use adequate contraception (hormonal / barrier method

of birth control or abstinence) prior to study and for the duration of the study participation. During the screening phase of this study, participants of childbearing potential will be administered a pregnancy test; a negative pregnancy test will be required to confirm eligibility for study participation and will be done prior to receiving ketamine. If a participant becomes pregnant or suspects she is pregnant while participating in the buprenorphine/placebo phase of the study, she should inform the research staff immediately via in-person meeting, telephone call, or email. If a participant reports pregnancy occurring during the study period in which the participant was exposed to buprenorphine/placebo, research staff will stop the study visit and then notify the principal investigator.

9. Statistical Considerations:

Null hypothesis statistical testing (NHST) and p-values were planned only for the pre-specified primary (SSI suicidality scores) and secondary efficacy measure (MADRS and HDRS depression scores) to minimize type 1 error risk. For any supplemental analyses (e.g, clinical endpoints), NHST is only employed if the prespecified efficacy analyses are statistically significant. For all research questions, effect sizes rather than p-values are emphasized. Effect size for the prespecified efficacy endpoints will use Glass's delta estimate, a variant of Cohen's d that corrects for the unequal variances often observed in intervention studies. Effect size for clinical analyses with a dichotomous outcome will be expressed as Number Needed to Treat (NNT).

Analysis of baseline characteristics: Demographic data including age, gender, ethnicity, diagnosis, treatment history, and previous suicide attempts will be summarized using descriptive statistics (means, standard deviation, range for continuous variables and frequency counts for categorical variables). Mean baseline scores on primary and secondary symptom measures (e.g., SSI, MADRS) as well as other related measures will be presented in a table. These demographics will be provided for the ITT all patients randomized and for the mITT efficacy evaluation sample.

Analysis of primary endpoint: The primary endpoint of this RCT, submitted a priori in clinical trials.gov, is reduction in SSI suicidality score from baseline to day 31. All randomized participants received a standard ketamine infusion, and SSI will be assessed at day 1 prior to the infusion and at day 3. Subsequently, patients will receive 4 weeks of either daily low-dose buprenorphine or placebo with doses increased weekly accompanied by weekly clinical assessments. H0, the null hypothesis, is that mean SSI suicidality ratings will not differ between patients randomized to low-dose buprenorphine and patients randomized to placebo. The research hypothesis H1 is patients randomized to the buprenorphine condition will have significantly lower SSI scores by the end of treatment (day 31). Null hypothesis testing and p-values were planned only for the primary and secondary hypotheses with consideration of type 1 error risk. For all analyses, effect sizes will be emphasized using Glass's estimate, a variant of Cohen's d that corrects for the unequal variances often observed in intervention studies or Number Needed to Treat.

Statistical analysis of the primary outcome will be based on the modified intention to treatment (mITT) population, defined as participants who received at least one SSI assessment during the active

treatment phase. Although ITT estimates theoretically have less bias, the mITT is a conservative decision for the current design in which all patients will first receive ketamine. Including patients who only received ketamine and completed no assessments past the ketamine phase (days 1 to 3) would provide no information regarding response to follow-on buprenorphine or placebo. Moreover, given the known antidepressant effect of ketamine on suicide, their inclusion would likely underestimate the projected means at time points during the post-ketamine evaluation of 4 weeks of follow-on buprenorphine vs placebo.

Repeated measurements of the SSI will be compared across treatment groups using a linear mixed-effects model. The mixed model makes use of all available SSI scores across the study timepoints to estimate group differences in means. The model will include fixed effects of treatment group, time, time by treatment group interaction, and a random effect of participant intercept. An unstructured covariance matrix, or a first order auto-regressive structure, will be used based on relative model fit according to the information criterion index. This model parameterization is suited for testing of between-group differences over repeated measurements, consistent with the primary study hypothesis. The SPSS syntax is:

MIXED SSI with time treatment

/Criteria=CIN(95) MXITER(100) MXSTEP(10) SCORING(1)

SINGULAR (0.0000000001) HCONVERGE(0, ABSOLUTE) LCONVERGE(0, ABSOLUTE),
PCONVERGE(0.00000001, ABSOLUTE)

/FIXED time time*treatment | SSTYPE(3)

/METHOD=ML

/RANDOM=INTERCEPT time | PARTICIPANT COVTYPE(UN).

The result of the hypothesis test for efficacy of Ketamine followed by Buprenorphine will be determined by the statistical significance of the treatment by time interaction (two-sided $\alpha=.05$). Only if group differences are deemed statistically significant on the prespecified primary outcome, a supplemental analysis of clinical significance will be conducted by calculating the proportion of responders, defined as a 50% or greater reduction in SSI suicidality ratings from baseline to day 31, in each of the two treatment groups. These proportions will be compared with a 2x2 chi-squared test.

